## **4. SELECTION AND WITHDRAWAL OF PARTICIPANTS**

### **4.1 PRE-RANDOMISATION OR PRE-REGISTRATION EVALUATIONS**

Mass treatment of the whole community with azithromycin is recommended for the purpose of yaws control. Mass treatment of the whole community with Ivermectin and Permethrin is the best available treatment for the purpose of scabies control. Both treatment are offered to all individuals regardless of the presence/absence of clinical features of either disease – which is in line with the best evidence on how community mass treatment for these diseases should be conducted.

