### **4.2 INCLUSION CRITERIA**

All consenting individuals in the participating communities will eligible to participate

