#### Topical 5% permethrin cream (Lyclear®)

Topical 5% permethrin (Lyclear®) cream for scabies is supplied in a 30g tube. The cream is applied all over the body including from neck to toe and washed off after a minimum of 8 hrs. For children aged 2 months or less permethrin should be washed off after 4 hours.

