### 6.2 Legal status of drug

Azithromycin is licensed for use in the UK. It is listed on the essential medicines list of the Solomon Islands and is the WHO recommended drug for community mass treatment for yaws eradication.

Permethrin is licenced in the UK for the treatment of scabies. It is listed as on the essential medicines list for the Solomon Islands and recommended as a potential treatment for scabies.

Ivermectin is not licenced for the treatment of scabies in the UK although NICE has provided guidance on its use (<https://www.nice.org.uk/advice/esuom29/resources/ivermectin-for-difficulttotreat-scabies-17546902981>). Ivermectin is widely used in control programmes for both Onchocerciasis and Lymphatic Filariasis. Ivermectin is listed as on the essential medicines list for the Solomon Islands and recommended as a potential treatment for scabies.

**6.3** Summary of Product Characteristics (SmPC) or Investigator Brochure (IB)  
Product Characteristics Sheets are attached in the Appendix.

**6.4** Drug Storage and Supply  
Medications will arrive by plane and will reach the islands by boat at the provincial pharmacy / medical store. The order request will be checked with the supplies delivered. The delivery notice number, delivery date and the medications batch number will be recorded in a log book. Medications will be taken out of the pharmacy in bulk by the study teams for dispensing in the community. Study teams will maintain a log of all medicines dispensed that can be cross-checked against participants study records.

**6.5** Preparation and labelling of IMP  
For participants receiving ivermectin and azithromycin, the dose will be determined according to body weight and treatment will be administered under direct supervision of the study team. Drug administration will be recorded in a standardized record form.

Participants assigned to permethrin (due to contra-indication to ivermectin) will receive a tube of cream and will be asked apply the cream from neck to toes before they leave the clinic and under supervision of a study nurse, and leave it on for a minimum of 8 hours, maximum 24 hours if possible. For children aged 2 months or less, cream will applied for a maximum of 4 hours.

**6.6** Dosage schedules/modifications  
In line with standard treatment the dosing of both Azithromycin and Ivermectin will use the following weight bands

WEIGHT	AZITHROMYCIN TABLETS (250mg Tabs)	IVERMECTIN TABLETS (3mg Tabs)
<15KG	1	PERMETHRIN CREAM

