12.5-15 – 25 KG	1	1
25 – 37.5 KG	2	2
37.5 – 50 KG	3	3
50-75 KG	4	4
>75 KG	4	5

Formatted: Font: Bold

Permethrin will be used instead of Ivermectin in the following circumstances

- Pregnancy
- Breastfeeding
- Child <6 months age
- Child <12.5kg

Formatted: Font: Bold

Where permethrin is indicated the following standard dosing protocol will be used:

- Full tube for adults.
- Half tube for children.
- Apply to whole body and leave on for 1 day before washing off

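### The permethrin schedule in Section 6.6 gives one contact time of 1 day and omits the protocol's own 4-hour limit for children aged 2 months or less

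*Combined protocol and SAP*

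**What the plan says.** Three parts of Section 6 give a contact time for permethrin cream.

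- **Section 6.1** (product description) has a general minimum of 8 hours and a separate rule for the youngest: "For children aged 2 months or less permethrin should be washed off after 4 hours".
- **Section 6.5** (preparation and labelling) tells participants in general to "leave it on for a minimum of 8 hours, maximum 24 hours if possible" and then adds: "For children aged 2 months or less, cream will applied for a maximum of 4 hours".
- **Section 6.6** (dosage schedules) opens its permethrin instructions with "Where permethrin is indicated the following standard dosing protocol will be used". It separates adults from children by amount of cream only (full or half tube). Its one statement on time is "Apply to whole body and leave on for 1 day before washing off".

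The groups that Section 6.6 assigns to permethrin include "Child <6 months age". Section 4.2 sets no lower age limit: "All consenting individuals in the participating communities will eligible to participate". Section 4.1 adds that "Both treatment are offered to all individuals regardless of the presence/absence of clinical features of either disease".

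**The concern.** For a child aged 2 months or less, Sections 6.5 and 6.6 cannot both be followed. Section 6.6 is headed as the dosing schedule, says that its regimen will be used, and comes last of the three, so it is a natural source for a field card or a training sheet. The infant limit sits in a product description and in a section on preparation and labelling.

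What is at stake is the exposure of the youngest participants, including infants without scabies, since treatment does not depend on clinical signs. Under Section 6.5 the cream is put on at the clinic under a nurse's supervision and the family then leaves, so washing off falls to the carer. No supervision of that step is described, and Section 6.10 assesses compliance only when the drug is given out. The time the carer is told is therefore the main visible control.

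A departure would also be hard to see afterwards. Section 7.3.1 limits collection to SAEs and SUSARs, Section 10.1 provides passive monitoring only, and Section 12 appoints no DSMB.

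**Working it through.** No statistical quantity is involved, so the check is a comparison of the texts followed by simple arithmetic.

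**1. Are these infants in the trial?** Section 4.2 has no lower age limit. The exclusion list under Section 5.1 removes people with a contra-indication to treatment. That does not remove young infants, because Sections 6.1 and 6.5 give them a regimen of their own. The protocol expects to treat them.

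**2. Does Section 6.6 apply to them?** A child aged 2 months or less is under 6 months, so Section 6.6 assigns permethrin. Its regimen covers every case in which permethrin is indicated, and its only adult/child distinction is the quantity of cream.

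**3. Contact times side by side**

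| Section | Children aged 2 months or less | Everyone else on permethrin |
|---|---|---|
| 6.1 | wash off after 4 h | at least 8 h |
| 6.5 | at most 4 h | 8 to 24 h |
| 6.6 | 1 day (no exception) | 1 day |

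**4. Size of the conflict, taking 1 day = 24 h**

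- Children aged 2 months or less: 24 / 4 = 6 times the Section 6.5 maximum. Excess per application: 24 − 4 = 20 h.
- Everyone else: 24 h against an upper limit of 24 h, so 24 − 24 = 0 h over.
- Two applications are planned, 7 to 14 days apart. The excess could therefore reach 2 × 20 = 40 h for an infant still in the age group at the second one.

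**5. Does the result depend on reading 1 day as exactly 24 hours?** No. Even the general 8-hour minimum in Sections 6.1 and 6.5 is 8 / 4 = 2 times the infant limit, and any ordinary reading of 1 day is longer than 4 hours.

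The documents do not give the number of residents aged 2 months or less, so the number of infants affected cannot be calculated.

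**The case against.** The strongest reply is that the matter is already handled. The 4-hour rule appears twice, the second time just before Section 6.6 in the paragraph that describes how the cream is given. On ordinary reading a specific age rule qualifies a general one, and a nurse is present when the cream is applied. On this view all that is missing is a cross-reference. This reading is reasonable, and it shows that the intended limit is 4 hours. It is not compelled: the protocol states no order of precedence, and Section 6.6 does not say that it yields to Section 6.5.

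The second reply is that no consequence is shown. This stands as a limit on the claim. The documents describe no specific harm from longer contact, and the number of infants is unknown. The MDA record form and the permethrin SmPC (Appendices 4 and 9) are not visible and may carry the correct instruction. The 6-fold figure measures the gap between two written instructions and is not a forecast of actual exposure.

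The body area to be treated is also worded differently in Sections 6.1, 6.5 and 6.6. That is a separate, minor matter which the visible text cannot settle, and nothing here rests on it.

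**Conclusion.** The point holds as an internal inconsistency in infant dosing. For children aged 2 months or less, the schedule in Section 6.6 permits 6 times the contact time allowed by Section 6.5, 20 hours over the limit per application. No other group is affected.

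The size rests on reading 1 day as 24 hours; the existence of the conflict does not. Confidence is high that the texts disagree. Whether any infant would be over-exposed depends on which text reaches field staff and carers, and the documents do not show that.

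The sample size, the primary outcome and the comparison between arms are untouched, because both arms receive the same scabies treatment. The point should be corrected because it concerns the youngest participants and the protocol contradicts a limit that it sets itself.

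**What to change.** Add an exception to the last permethrin bullet in Section 6.6, for example: *except children aged 2 months or less: wash off after a maximum of 4 hours (see Section 6.5); tell the carer the wash-off time.* Check that the MDA record form (Appendix 4) and any field card or training material drawn from Section 6.6 carry the same limit.

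The cost is one clause in the protocol, a check of the forms, and one spoken instruction to each carer of an infant in this age group. It needs no extra visit, staff or drug, and no change to the analysis.

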## 6.7 Known drug reactions and interaction with other therapies

The safety profile of both azithromycin and ivermectin is well established from large mass treatment campaigns where >100 million doses have been administered. The most commonly reported side effects for Ivermectin are headache, dizziness, itch. For Azithromycin the most commonly reported side effects are abdominal pain, nausea, vomiting and diarrhoea. For both drugs adverse events are normally mild and self-limiting with no specific therapy required.

Results from a pharmacovigilance study involving more than 3,000 participants on the adverse events associated with the triple, co-administered combination therapy of azithromycin, ivermectin and albendazole (AZIVAL, AZithromycin, IVermectin, ALbendazole) in Mali found that triple combination therapy appears to be safe[14]. There were no serious adverse events in this study. Overall the rate of adverse events was similar in the triple combination therapy group (18.7%) compared to the standard therapy group (16.0%). Taken together these studies support expert opinion that the combination of azithromycin and ivermectin is safe.

## 6.8 Concomitant medication

Individuals receiving Warfarin may not receive treatment with Ivermectin due to potential interactions.

No individuals outside of the capital of the Solomon Islands (Honiara) are receiving Warfarin due to a lack of INR monitoring facilities and therefore it is not anticipated that any individuals in the study will be receiving a contra-indicated concomitant medication.

**6.9** Trial restrictions

There are no trial restrictions.

As noted above pregnant and breast feeding women and children <15kg will be offered permethrin rather than ivermectin but will still be allowed to participate in the study.

**6.10** Assessment of compliance

Drugs will be delivered as a single observed treatment and therefore compliance will be assessed at the time of drug distribution.

## 7. SAFETY REPORTING FOR DRUG TRIALS

### 7.1 DEFINITIONS

Term	Definition
Adverse Event (AE)	
Any untoward medical occurrence in a participant to whom a medicinal product has been administered, including occurrences which are not necessarily caused by or related to that product.
 
An AE can therefore be any unfavourable and unintended sign (including an abnormal laboratory finding), symptom, or disease temporally associated with the use of an investigational medicinal product (IMP), whether or not considered related to the IMP.

Adverse Reaction (AR)	
Any untoward and unintended response in a participant to an investigational medicinal product which is related to any dose administered to that participant.
 
The phrase “response to an investigational medicinal product” means that a causal relationship between a trial medication and an AE is at least a reasonable possibility, i.e. the relationship cannot be ruled out.
 
All cases judged by either the reporting medically qualified professional or the Sponsor as having a reasonable suspected causal relationship to the trial medication qualify as adverse reactions.

Serious Adverse Event (SAE)	
A serious adverse event is any untoward medical occurrence that:
 
 
• Results in death
 
• Is life-threatening
 
• Requires inpatient hospitalisation or prolongation of existing hospitalisation
 
• Results in persistent or significant disability/incapacity
 
• Consists of a congenital anomaly or birth defect
 
 
Other ‘important medical events’ may also be considered serious if they jeopardise the participant or require an intervention to prevent one of the above consequences.

Serious Adverse Reaction (SAR)	
An adverse event that is both serious and, in the opinion of the reporting investigator, believed with reasonable probability to be due to one of the trial treatments, based on the information provided.

Suspected Unexpected Serious Adverse Reaction (SUSAR)	
A serious adverse reaction, the nature and severity of which is not consistent with the information about the medicinal product in question set out:
 
 
• In the case of a product with a marketing authorisation, in the summary of product characteristics (SmPC) for that product
 
• In the case of any other investigational medicinal product, in the investigator brochure (IB) relating to the trial in question.
 

### 7.2 CAUSALITY

Most adverse events and adverse drug reactions that occur in this study, whether they are serious or not, will be expected treatment-related side effects due to the drugs used in this study. The assignment of causality should be made by the investigator responsible for the care of the participant using the definitions in the table below.

If any doubt about the causality exists the local investigator should inform the study coordination centre who will notify the Chief Investigators. The pharmaceutical companies and/or other clinicians may be asked to advise in some cases.

In the case of discrepant views on causality between the investigator and others, all parties will discuss the case. In the event that no agreement is made, both points of view are to be reported.

Relationship	Description
Unrelated	There is no evidence of any causal relationship
Unlikely	There is little evidence to suggest there is a causal relationship (e.g. the event did not occur within a reasonable time after administration of the trial medication). There is another reasonable explanation for the event (e.g. the participant's clinical condition, other concomitant treatment).
Possible	There is some evidence to suggest a causal relationship (e.g. because the event occurs within a reasonable time after administration of the trial medication). However, the influence of other factors may have contributed to the event (e.g. the participant's clinical condition, other concomitant treatments).
Probable	There is evidence to suggest a causal relationship and the influence of other factors is unlikely.
Definitely	There is clear evidence to suggest a causal relationship and other possible contributing factors can be ruled out.
Not assessable	There is insufficient or incomplete evidence to make a clinical judgement of the causal relationship.

### 7.3 REPORTING PROCEDURES

Depending on the nature of the event the reporting procedures below should be followed. Any questions concerning adverse event reporting should be directed to the study coordination centre in the first instance.

#### 7.3.1 Non serious Adverse Reactions (ARs)/Adverse Events (AEs)

Given the established safety profile of the drugs being used in this study and the fact that they are being used for established indications we will only collect data on SAEs and SUSARs.

#### 7.3.2 Serious Adverse Reactions (SARs)/Serious Adverse Events (SAEs)

Serious Adverse Events (SAEs) and Serious Adverse Reactions (SARs) should be reported to the study coordination centre within 24 hours of the local site being made aware of the event.

An SAE form should be completed and submitted to the study coordination centre with as much detail of the event that is available at that time. If awaiting further details, a follow up SAE report should be submitted promptly upon receipt of any outstanding information. The CI (for a single-centre trial) or PI (for a multi-centre trial) must record the event with an assessment of seriousness, causality and expectedness.

Any events relating to a pre-existing condition or any planned hospitalisations for elective treatment of a pre-existing condition do not need reporting as SAEs.

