### *Site 2- Serial Treatment Arm*

Ivermectin/Permethrin (for scabies) will be offered on D1 with a second dose of Ivermectin/Permethrin offered 7-14 days later..

Single dose azithromycin (for yaws) will be offered at the twelve month follow-up visit.

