#### 7.3.3 SUSARs

All SAEs assigned by the PI or delegate as both suspected to be related to IMP-treatment and unexpected will be classified as SUSARs and will be subject to expedited reporting to the Regulatory Authority, in the UK: Medicines and Healthcare Products Regulatory Agency (MHRA). The Sponsor (or delegate) will inform the MHRA, and the ethics committee of UK-relevant SUSARs within the required expedited reporting timescales (as per LSHTM Standard Operating Procedure for recording, managing and reporting of adverse events for IMP studies).

For blinded trials, all SUSARs must be reported assuming the active compound is involved.

In the case of a suspected, unexpected, serious adverse reactions (SUSAR), the staff at the site should:

1. Contact the study coordination centre immediately by phone or email to inform them of the event.
2. Submit a completed SAE form (signed and dated) within 24 hours, together with relevant treatment forms and anonymised copies of all relevant investigations.
3. Submit any additional information promptly upon request.

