### Interim Visit

At Month 3 an interim visit will be made. Individuals will be re-examined and swabs collected from those with clinical evidence of impetigo. Data from previous studies indicates that scabies and impetigo continue to decline between month 3 to month 12 following community mass treatment for scabies therefore treatment will not routinely be offered at this time point.

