## 9. STATISTICS AND DATA ANALYSIS

### *Sample Size*

The sample size required for our primary outcome was estimated as follows:

- Pre-MDA prevalence of impetigo of 25-30%
- Impetigo prevalence to fall to about 10% in the Ivermectin only arm
- Impetigo prevalence to fall to about 5% in the combined arm
- Enrolment 80%
- Loss to follow-up 10%
- 90% power to detect a difference between the two arms

Primary Outcome:

- a) Prevalence of impetigo at months 12 months in parallel treatment communities compared to sequential treatment communities.

Secondary outcomes:

- b) Change in the proportion of swab samples from which *S. pyogenes* is cultured between baseline and follow-up in the two arms
- c) Proportion of samples from which a drug-resistant isolate is cultured.

Data and all appropriate documentation will be stored for a minimum of 5 years after the completion of the study, including the follow-up period.

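### Section 7.3.2 exempts every event related to a pre-existing condition from SAE reporting, so a serious complication of a baseline impetigo or yaws lesion could go unreported

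*Combined protocol and SAP*

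**What the plan says.** The safety rules in section 7 of the combined protocol and SAP fit together as follows.

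- **Definition (7.1).** The SAE entry opens "A serious adverse event is any untoward medical occurrence that" and then lists death, threat to life, inpatient admission, lasting disability and congenital anomaly. It makes no exception for disease present before treatment.
- **Reporting (7.3.2).** SAEs and serious adverse reactions "should be reported to the study coordination centre within 24 hours of the local site being made aware of the event". The section closes with the exemption: "Any events relating to a pre-existing condition or any planned hospitalisations for elective treatment of a pre-existing condition do not need reporting as SAEs".
- **Other adverse events (7.3.1).** Given the drugs' established safety profile and indications, "we will only collect data on SAEs and SUSARs".
- **SUSARs (7.3.3).** SAEs judged "both suspected to be related to IMP-treatment and unexpected will be classified as SUSARs".

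Three other parts of the plan bear on the point. In section 3, under the serial treatment arm, "Single dose azithromycin (for yaws) will be offered at the twelve month follow-up visit". In section 8, the Day 1 examination records lesions consistent with yaws, scabies and impetigo in every participant, and at the month 3 interim visit "treatment will not routinely be offered at this time point". Section 10.1 provides for passive adverse event monitoring only, and section 12 states that no DSMB will be appointed.

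**The concern.** Exempting planned elective admissions for a stable condition is routine. The first half of the sentence in 7.3.2 goes much further, and in this trial the breadth matters because the conditions people already have on Day 1 include the diseases under study. A person with an impetigo lesion at baseline who is later admitted as an emergency, or dies, from an infection arising from that lesion has had an event that relates to a pre-existing condition. On the wording, a site need not report it.

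The design sharpens this. The arms differ in whether azithromycin is offered on Day 1 or at month 12, and the primary objective is whether azithromycin has an added effect on impetigo. Serious bacterial complications of skin lesions are thus one plausible harm of deferral. The plan justifies its light safety collection by the known profiles of the drugs, which is an argument about drug toxicity and does not address harm from waiting. At stake is whether the trial's only safety data could show such harm if it occurred.

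**Working it through.** No figure in the plan depends on this rule, so the check is mainly textual. One calculation gives scale.

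**1. Scope of the exemption.** The sentence in 7.3.2 has two limbs joined by *or*. The words that restrict it to planned admissions and elective treatment sit in the second limb. The first limb stands alone, with no condition on severity, worsening, type of admission or outcome.

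**2. Whether baseline lesions fall within it.** The protocol does not define a pre-existing condition and does not exclude impetigo, yaws or scabies from the term. Section 8 has these lesions recorded on Day 1 before treatment is given, so they are documented as already present. The plain meaning includes them.

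**3. Whether another route captures the event.**

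| Route | Section | Captures serious worsening of a baseline lesion? |
|---|---|---|
| SAE report | 7.3.2 | Not required, under the first limb |
| Non-serious AE record | 7.3.1 | No; not collected |
| SUSAR report | 7.3.3 | No, unless suspected to be drug-related and unexpected |
| Active surveillance | 10.1 | None; monitoring is passive |
| Independent board | 12 | None appointed |
| Month 3 and month 12 visits | 8 | Examination and sampling are described; asking about deaths or admissions between visits is not |

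On the last row, a participant who died could appear only as lost to follow-up, for which section 9 allows 10%.

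**4. Size of the group concerned.** Inputs: 637 per arm (Study Summary) and "Pre-MDA prevalence of impetigo of 25-30" per cent (section 9, Sample Size).

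People per arm with baseline impetigo = arm size × baseline prevalence.

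- Lower: 637 × 0.25 = 159.25, about 159
- Upper: 637 × 0.30 = 191.1, about 191
- Both arms (2 × 637 = 1,274): 1,274 × 0.25 = 318.5 and 1,274 × 0.30 = 382.2, about 319 to 382

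The background (section 1.1) cites recent national surveys with impetigo at up to 40%. At that value the count would be 637 × 0.40 = 254.8, about 255 per arm. The documents give no yaws prevalence for the study communities, so no count is offered for yaws.

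**5. What cannot be computed.** Missed events = people with a baseline lesion × probability of a serious complication × probability that the site uses the exemption. The documents give neither probability, so no number of missed events follows.

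**The case against.** **Permission is not prohibition.** The text says that such events need not be reported. A site may still report them, may treat an invasive infection as a new occurrence under 7.1, or may ask the coordination centre, to which 7.3 directs questions. This stands: the events *could* go unreported, and a reader who infers that they *would*, or that capture is nil, goes beyond the text. It does not remove the defect, because reporting a serious complication of a study disease should not depend on site discretion, least of all in an open-label trial where discretion could differ by arm.

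**No contradiction.** It is tempting to set 7.1 against 7.3.2 as conflicting. They do not conflict: one defines an SAE, the other limits which SAEs must be reported. The fault is the breadth of the exemption.

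**The rule is symmetric and partial.** It applies to both arms. At 25-30% prevalence, 70-75% of participants have no baseline impetigo, so an impetigo-related serious event in them is not exempted on that ground. Impetigo is also expected to fall to about 10% and 5%, and an event from a later, new lesion is not plainly pre-existing. All of this stands and narrows the gap to complications of lesions present on Day 1.

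**Deferral harm is not established.** A reader might infer that serious skin infection is the harm most likely to differ between arms, or that the trial would wrongly report no serious events. The documents support neither: safety is not a stated objective or outcome, and the study is classed as low risk. Scabies adds nothing to the deferral argument, since both arms are offered scabies treatment on Day 1.

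**Other documents may help.** Section 7.3.3 cites a sponsor procedure on adverse events and the appendices list an SAE form. Either might narrow the exemption, but the protocol does not say so.

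**Conclusion.** The point holds as a gap in safety capture. Followed as written, 7.3.2 allows a serious complication of an impetigo or yaws lesion present on Day 1 to go unreported, and no other route described in the protocol would pick it up, in a trial where one arm is not offered azithromycin until month 12.

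About 159-191 people per arm fall within the exemption for impetigo-related events. That count assumes that 637 are examined per arm and that prevalence is 25-30% as planned. It should not be read as a count of lost events, which may be small. The conclusion also rests on the ordinary meaning of an undefined term and on the protocol text alone, without the sponsor procedure or the SAE form.

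This should be fixed, but it does not threaten the trial's main result: randomisation, sample size, the primary outcome and its analysis are unaffected.

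**What to change.** In 7.3.2, delete the first limb of the exemption and restrict what remains. Suggested wording: *Planned admissions for elective treatment of a condition that was present before Day 1 and has not worsened since then need not be reported as SAEs.* Then add: *Serious worsening of a condition present at baseline, including impetigo or yaws, is reportable as an SAE in both arms.* Carry the same wording into the SAE form and site guidance.

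This alters reporting only, not treatment. The cost is one edited sentence, one added sentence and a few more SAE forms.
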